NCT03502265

Otteroo Case Series

Uploaded September 28, 2021

IRB approval date: 3/8/2018. University of Southern California Health Sciences Institutional Review Board (HS-17-00910)

Protocol

Significance and justification for use

The goal of this project is to measure overall developmental status before and after Otteroo experience in pre-locomotor infants and young children for whom a healthcare provider or caregiver has identified concerns about potential developmental delay. We are proposing that the Otteroo may be a good “tool” to facilitate early movement and exploration of the ability to move and control one’s body. The Otteroo is a widely-available commercial floatie marketed to families as “a floatie for babies ages 8 weeks +” (<https://otteroo.com/>).

The Otteroo is a floatie which supports an infant or young child with their head above and their body in water. The Otteroo allows them to move around in water under direct caregiver supervision and within arm’s reach without the need for the caregiver to physically support the infant or child. As water provides a reduced-gravity environment, it allows infants and young children an opportunity to explore their ability to move and control their bodies more easily than when they are in a ‘typical gravity’ environment. Research has shown that infants are initially able to move their limbs against gravity in a stepping pattern, then go through a period of rapid weight gain that is not matched by a concurrent strength gain, and thus ‘lose’ the ability to step against gravity as they are not strong enough to lift their heavier limbs. Supporting them in water, however, allows them to perform stepping movements during the period when they otherwise would not be strong enough (1). While typically-developing infants move through this developmental progression, infants with motor delays can get ‘stuck’ in this period. As a result of their difficulty moving, they continue to physically grow but may not gain the requisite strength and may not optimally explore their ability to move and control their bodies during this foundational early developmental period (2). Children with developmental delays and disabilities are often recommended to participate in aquatic therapy to supplement clinic, early intervention, or school-based physical therapy or occupational therapy. One study with 37 children ages 6-30 months found that the aquatic therapy plus standard early intervention group demonstrated significantly greater gains in functional mobility than the comparison group of children who received standard early intervention only (3). Further, aquatic therapy has been explored as a useful intervention in clinically stable newborns of gestational age less than 36 weeks who were hospitalized in a neonatal intensive care unit (4). We propose that using the Otteroo to allow movement practice in a reduced-gravity environment will allow infants to perform leg movements they otherwise would not be strong enough to perform, and this increased exploration and movement practice may have a positive impact on their development.

Approach

A pilot study sample of up to 4 infants/young children will participate. A single-subject research design will be used: measures of infant development will be collected across a 4-week baseline period (standard care), 4 weeks of intervention (standard care and Otteroo use), and 4 weeks of reversal/retention period (standard care).

Inclusion Criteria: Infants and young children who are pre-locomotor and for whom a healthcare provider or caregiver has identified concerns about potential developmental delay (see appendix 1).

Exclusion Criteria: Infants younger than 8 weeks of age or with body weight of more than 35 lbs will be excluded per the specifications of use of the Otteroo floatie. Children who are able to locomote independently more than 4 feet will be excluded as prelocomotor infants and young children are the target. Children older than 66 months of age will be excluded do to restrictions of the Ages and Stages measurement tool. Infants or children with a diagnosis of Down syndrome or with a clinical presentation of ligamentous laxity will be excluded due to concerns about atlanto-axial instability. Infant or children without access to an appropriate water source (bathtub or pool depending on the size of the child) will be excluded. Infants or children with prior experience using Otteroo will be excluded.

Participant Recruitment:

The infants will be recruited using fliers distributed at Starfish Therapies, an early intervention therapy provider in San Mateo, CA. Starfish therapies may give handouts to potential participants they identify through looking at their own clinic's medical records or by looking at their own clinic logs. They are a pediatric clinic with 6 physical therapists, and see approximately 10 patients per week who meet our inclusion criteria. The caregivers will be asked to contact the research staff by phone or email for further information about the research study, including discussion of the exclusion criteria. When caregivers contact the research staff, the staff will give more specific information about the study and answer any questions. If the caregivers choose to participate after the initial contact, a written consent form will be provided to them. This will allow them to discuss their participation with others before signing the written consent. A parental consent form will be signed by a parent or legal guardian at the first visit, before any study procedures occur.

Procedures: Visits will take place at Starfish Therapies and last approximately 30 minutes.

At the first visit (week 0), the researcher will measure the participant's weight, overall development, and motor development. The researcher will assess and quantify motor development by administering the Alberta Infant Motor Scale, a standardized, norm-referenced observational scale of motor development (5). The researchers will assess and quantify overall development using the Ages and Stages Questionnaire,

a standardized, norm-referenced caregiver-report scale of development (6). This is standard of care.

At the second visit, after a 4-week baseline period (week 4), the researcher will measure the participant's weight and administer the Alberta Infant Motor Scale and the Ages and Stages Questionnaire. This is standard of care. The researcher will provide an Otteroo floatie to the family, along with an activity log to track its use. Caregivers will report date of use, duration of use, activities performed, and child's response. The researcher will refer the family to the Otteroo website for some ideas of potential activities, as well as discuss and determine potential activities with the family. The researcher and family will use the Canadian Occupational Performance Measure (7), a standardized method for setting an individual goal, to set a goal relating to Otteroo use. The researcher will document therapy services received, and briefly describe the amount and type of any therapy received. This is for research purposes.

After 4 weeks of Otteroo use (week 8), the researcher will collect the Alberta Infant Motor Scale, the Ages and Stages Questionnaire (all standard of care), and the Canadian Occupational Performance Measure (research purposes). The researcher will collect the activity log (research purposes). The researcher will document therapy services received, and briefly describe the amount and type of any therapy received (research purposes). The family will answer survey questions about their experience with Otteroo (research purposes). The family will keep the Otteroo floatie.

After 4 weeks of reversal/retention period (week 12), the researcher will administer the Alberta Infant Motor Scale and the Ages and Stages Questionnaire. This is standard of care.

Data Analysis. We will calculate descriptive statistics (mean, range, coefficient of variation) for all measures and describe the participants over time. The Alberta Infant Motor Scale is the primary outcome. We will relate the participant's performance at each time point to norm-referenced results for their age. We will compare rate of change of Alberta Infant Motor Scale between weeks 0 and 4, 4 and 8, and 8 and 12. The Canadian Occupational Performance Measure is a secondary outcome measure, and we will report whether or not goals are met between weeks 4 and 8.

Potential risks

The infant or young child may become distressed during data collection or Otteroo use. The caregiver may stop any activity at any time and soothe the infant or child.

There is a small risk that the Otteroo will deflate while the child is using it (due to leaks or seams breaking), and being in water carries risk of drowning. The caregiver must directly supervise and be within arm's reach of the child while he or she uses the floatie. If it starts to deflate, the caregiver has been instructed in the consent form to stop using it and re-inflate it before resuming use. If it deflates again, we will replace it.

Protections

Loss of confidentiality will be minimized by identifying all research data with the participant's study identification number, and allowing only those authorized to have access to the data. REDCap, a university supported, secure data collection and storage site will be used for collecting and storing the participant's randomly generated study identification code number and identifying information and health information. All other files will be identified by code numbers only, not by name or by any other information which might identify the parent or participant. All data will be on secured, password protected, backed up USC servers at all times.

References

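### The prior-exposure exclusion names one brand, so a child already using an equivalent floatie can enter, and home water use in weeks 0-4 is not recorded

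*Combined protocol and SAP*

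**What the plan says.** Under Approach, the Exclusion Criteria deal with earlier exposure in one sentence: "Infants or children with prior experience using Otteroo will be excluded". No listed criterion mentions other floaties, aquatic therapy or other supported time in water. A neighbouring criterion makes water access a condition of entry: "Infant or children without access to an appropriate water source (bathtub or pool depending on the size of the child) will be excluded".

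The Approach section sets out the phases: "measures of infant development will be collected across a 4-week baseline period (standard care), 4 weeks of intervention (standard care and Otteroo use"), followed by four weeks of reversal or retention on standard care. Standard care is not defined further.

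The section on significance and justification gives the rationale. It proposes that "using the Otteroo to allow movement practice in a reduced-gravity environment will allow infants to perform leg movements" that the infants would otherwise be too weak to make. It also says that "Children with developmental delays and disabilities are often recommended to participate in aquatic therapy", and cites a study of 37 children in which "the aquatic therapy plus standard early intervention group demonstrated significantly greater gains in functional mobility" than the comparison group.

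On records, Procedures states at weeks 4 and 8: "The researcher will document therapy services received, and briefly describe the amount and type of any therapy received". This is not listed for week 0 or week 12. The activity log is handed over with the floatie at week 4 and tracks use of that floatie.

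Data Analysis names the Alberta Infant Motor Scale as primary outcome and compares its rate of change over weeks 0-4, 4-8 and 8-12. It does not say how the therapy records will be used.

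**The concern.** By excluding earlier Otteroo users, the protocol accepts that earlier exposure matters. It then draws the line at a product name, although its mechanism belongs to water and body support. A child who already floats unaided in a similar device has essentially the exposure under study, and passes the criterion.

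For that child, weeks 0-4 may already contain part of the effect that weeks 4-8 are meant to show. Each child is their own control and there are at most 4 children, so a compromised baseline spoils that child's whole comparison. With no record of home water use before week 4, a reader of the results could not see that this had happened.

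**Working it through.** The protocol gives no figure to reproduce: it is a descriptive pilot with no alpha, power, effect size or standard deviation. The check sets the passages side by side and then shows the direction of the effect.

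**Step 1. Which exposures are kept out or recorded?**

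| Exposure | Excluded at entry? | Recorded for weeks 0-4? | Recorded for weeks 4-8? | Recorded for weeks 8-12? |
|---|---|---|---|---|
| Otteroo | Yes, if prior | Not applicable (supplied at week 4) | Yes, activity log | No record listed |
| Aquatic therapy as a service | No | Probably, therapy record at week 4 | Yes, therapy record at week 8 | No record listed |
| Another body-supporting floatie, or other supported water time at home | No | No | No | No |

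The entry "probably" reflects that Procedures does not state which period the week 4 record covers. The last row is the gap: neither excluded nor recorded in any phase.

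**Step 2. When does this change the comparison?** Let *g* be a child's rate of change on the motor scale without supported water movement, assumed equal in both phases. Let *d* be the gain in rate from Otteroo, *f* the assumed fraction of *d* that another floatie already provides, and *a* the gain from aquatic therapy. The contrast is the rate in weeks 4-8 minus the rate in weeks 0-4.

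- Other floatie replaced by Otteroo: (g + d) - (g + fd) = (1 - f)d. Diluted.
- Aquatic therapy stable and additive: (g + a + d) - (g + a) = d. Unchanged.
- Aquatic therapy starts at week 4: (g + a + d) - g = d + a. Inflated.
- Aquatic therapy stops at week 4: (g + d) - (g + a) = d - a. Deflated.

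**Step 3. Illustration, with *f* assumed.** For one affected child among 4, the mean contrast is [3d + (1 - f)d]/4 = (1 - f/4)d.

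| Assumed f | That child's contrast, 1 - f | Mean of 4 children, 1 - f/4 |
|---|---|---|
| 0.25 | 0.75 d | 0.9375 d |
| 0.5 | 0.50 d | 0.875 d |
| 1.0 | 0 | 0.75 d |

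The documents give no value for *f*, *a* or *d*, and no count of families who use other floaties. The table shows direction and range only. In a single-subject design the middle column matters more than the last.

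**The case against.** The best defence is that the question is an add-on one. The stated goal is development before and after Otteroo experience, the comparator is standard care, and excluding earlier users of that product fits. Aquatic therapy shares the mechanism but is a different intervention, and the device is described as letting the child move without being physically supported by the caregiver. Therapy of any kind is documented at weeks 4 and 8, so with at most 4 children a start or stop of aquatic therapy could be noticed child by child. The protocol does not say that any family uses another floatie.

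Most of this stands for aquatic therapy. A reader might infer, from the remark that it is often recommended and from recruitment at "an early intervention therapy provider in San Mateo, CA", that aquatic therapy contaminates the baseline and that such children should be excluded. The documents do not support that: a stable background therapy cancels within a child, no uptake figure is given, and exclusion would remove children for whom an add-on result is relevant. Nor does the clinic's figure of about 10 patients a week show that such a narrowing is affordable. It counts patients meeting the inclusion criteria, before exclusions, and may include the same children returning.

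The defence does not reach the equivalent floatie. That is not a therapy service, so the therapy record need not capture it, and it reproduces the device's function as well as its mechanism.

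**Conclusion.** The gap holds for equivalent floaties and unrecorded home water time. A child already using one is eligible, and that child's comparison of weeks 0-4 with weeks 4-8 is diluted if Otteroo takes its place. For aquatic therapy the problem arises only if it starts, stops or is displaced between phases. The therapy records may show this for the first two phases, but Data Analysis gives them no role.

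The size cannot be estimated from the documents. A reader might take the illustrative fractions as findings, but they rest on an assumed *f*, full replacement, and an otherwise constant rate of development. The trial is not invalidated. It is a descriptive pilot, and this is a cheap improvement to how each child's result can be read.

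**What to change.** 1. Extend the exclusion to prior or current use of any floatie that supports the body in water without the caregiver holding the child. Exclusion criteria are already discussed when families first make contact, so this adds one question there.
2. Keep children in aquatic therapy eligible. At the existing week 4, 8 and 12 visits, record aquatic therapy and other supported water time, in approximate minutes per week, for the phase just ended.
3. In Data Analysis, state that this record will be shown beside each child's rate of change for each phase. Any child whose non-Otteroo water exposure changed between phases should be flagged as one whose change in rate cannot be attributed to Otteroo alone.

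The cost is one or two caregiver-recall questions per visit, with the imprecision of recall, and a slightly narrower population. No visit or assessment is added. How many children the wider exclusion would remove cannot be judged from the documents.

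### Therapy received is recorded at weeks 4 and 8 but not at week 12, so the last of the three compared intervals has no record of background therapy

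*Combined protocol and SAP*

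**What the plan says.** The Approach section describes a single-subject design in up to 4 children with three 4-week phases: baseline, intervention with Otteroo use, and reversal/retention. Standard care runs through all three.

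For the week-4 visit, the Procedures section states: "The researcher will document therapy services received, and briefly describe the amount and type of any therapy received. This is for research purposes". The same task appears at week 8, again labelled as research. For the final visit it states: "After 4 weeks of reversal/retention period (week 12), the researcher will administer the Alberta Infant Motor Scale and the Ages and Stages Questionnaire". Both of those instruments are labelled standard of care, and no research item is listed at week 12.

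The Data Analysis section names the AIMS as the primary outcome and states: "We will compare rate of change of Alberta Infant Motor Scale between weeks 0 and 4, 4 and 8, and 8 and 12".

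**The concern.** In a single-subject design without a control group, an interval can be interpreted only against the same child's other intervals. That requires background care to be either stable or known. The protocol treats background therapy as worth knowing, since it collects it twice for research purposes. It stops before the last phase and gives no reason.

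Suppose a child's therapy increased, decreased or changed in type after week 8. The AIMS rate for weeks 8-12 could then differ from an earlier rate for that reason, and nobody reading the planned data could examine the possibility. The protocol's own rationale accepts that added therapy can matter: it cites a study of 37 children in which aquatic therapy on top of early intervention was followed by greater gains in functional mobility. It also notes, as general background, that such children may receive therapy through a clinic, early intervention or school. The recruiting clinic's own files would therefore not necessarily show a change.

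**Working it through.** The protocol gives no figure to reproduce. The check is a comparison of the visit schedule with the planned analysis.

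**Procedures by visit (Procedures section)**

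| Visit | AIMS and Ages and Stages Questionnaire | Therapy record |
|---|---|---|
| Week 0 | yes | no |
| Week 4 | yes | yes |
| Week 8 | yes | yes |
| Week 12 | yes | no |

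The therapy record is planned at 2 of 4 visits, for an analysis that uses 3 intervals.

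**Is therapy after week 8 captured elsewhere?**

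- The activity log tracks Otteroo use, not therapy, and is collected at week 8.
- Clinic records and logs appear only under Participant Recruitment, for identifying possible participants.
- The Protections section mentions health information stored in REDCap only in general terms.

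None of these supplies a therapy record for weeks 8-12.

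**Does the result depend on what period each entry covers?** The protocol does not state the period.

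- *Entries look back 4 weeks (assumption).* This is the natural reading, since the week-4 and week-8 visits each close a phase. Week 4 covers 0-4, week 8 covers 4-8, and nothing covers 8-12.
- *Entries describe services current at the visit.* Interval 0-4 has its end point only, 4-8 has both ends, and 8-12 has its start point only.

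On either reading, an entry made at week 8 cannot document therapy given afterwards.

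**Extent**

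- Time after the last entry: 12 − 8 = 4 weeks, and 4/12 = one third of each child's follow-up.
- Comparisons that use 8-12, under the look-back reading: with all pairs {0-4 v 4-8, 0-4 v 8-12, 4-8 v 8-12}, 2 of 3 lack a therapy record on one side. With adjacent phases only {0-4 v 4-8, 4-8 v 8-12}, 1 of 2 does. The Data Analysis section does not say which set is meant.

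These are counts of what is uncovered. The documents give no basis for the size of any effect on the AIMS rate.

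**The case against.** The omission itself is hard to dispute. The case on the other side is that it matters little.

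- *No planned analysis uses the therapy data.* This is true: the Data Analysis section never mentions therapy. But the data are collected for research purposes, and their evident use is to interpret the phase comparisons. The loss is to interpretation and not to a stated calculation.
- *Weeks 8-12 stay hard to read even with a therapy record.* This stands. At week 8 the protocol says "The family will keep the Otteroo floatie", and the only activity log has by then been handed in, so continued use in a phase described as standard care would go unrecorded. That is a second, separate unknown. A therapy entry does not remove it, but it does close the other one.
- *If entries are point-in-time, week 0 lacks one too.* This is fair. On that reading 0-4 and 8-12 each have one end recorded, and the clear contrast between covered and uncovered intervals depends on the look-back assumption. The absence of any record after week 8 does not.
- *Nothing suggests that therapy will change after week 8.* This is correct, and no such change is claimed. The point is that a change could not be detected.
- *The stakes are low.* This is a descriptive pilot in up to 4 children. Its stated goal of comparing development before and after Otteroo experience rests mainly on 0-4 versus 4-8, which is unaffected. That keeps the point minor without answering it.

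**Conclusion.** The concern holds, as a minor point. As written, the plan leaves the last 4 of 12 weeks without a therapy record while comparing the primary-outcome rate over those weeks with earlier rates. Confidence in the omission is high, and it does not depend on how the existing entries are read. The counts of affected comparisons (2 of 3, or 1 of 2) assume a 4-week look-back that the protocol does not state. No error rate, test or sample-size figure is affected, and no bias of any given size is asserted. An analyst could not recover the information later from the data the plan provides.

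**What to change.** Add the therapy-services record already used at weeks 4 and 8 (amount and type) to the week-12 visit, covering the preceding 4 weeks. State the period that the week-4 and week-8 entries cover as well, so that the three entries are comparable. In the Data Analysis section, say that therapy received will be shown with each child's AIMS rate for the same interval, as part of the description over time that is already planned.

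The cost is one question per child at an existing visit, 1 × 4 = at most 4 extra entries, with no added visit, staff or instrument. If the week-12 visits have already taken place without the record, say in the report that background therapy in weeks 8-12 was not documented, and interpret that interval accordingly. Either way, the report should also note that Otteroo use after week 8 was not logged, because the therapy record does not address that.

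### A floatie that deflates in use is re-inflated and used again, with replacement promised only if it deflates a second time; replacing it at the first would be safer at little cost

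*Combined protocol and SAP*

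**What the plan says.** The rule is in one paragraph under Potential risks in the combined protocol and SAP. That paragraph states the hazard and its causes: "There is a small risk that the Otteroo will deflate while the child is using it (due to leaks or seams breaking"), and it adds that water brings a danger of drowning. The standing safeguard is: "The caregiver must directly supervise and be within arm's reach of the child while he or she uses the floatie". For the response to a deflation, the paragraph points to an instruction given elsewhere: "If it starts to deflate, the caregiver has been instructed in the consent form". The content of that instruction, with the study's own promise after it, reads: "to stop using it and re-inflate it before resuming use. If it deflates again, we will replace it".

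Other sections give the context:

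- **Significance and justification for use** describes what the device does: "The Otteroo is a floatie which supports an infant or young child with their head above and their body in water". The child can move about "under direct caregiver supervision and within arm’s reach without the need for the caregiver to physically support the infant or child".
- **Approach** sets the scale: "A pilot study sample of up to 4 infants/young children will participate". The use phase is "4 weeks of intervention (standard care and Otteroo use").
- **Procedures** has each family receive one floatie at week 4 and keep it after the week 8 visit.

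**The concern.** The rule does not match the causes given two sentences before it. If air is lost through a leak or an opening seam, the defect is still there after the unit has been filled again. The first deflation is the warning that a unit may be defective, and the stated response lets that unit go back into use. The plan accepts that deflation is a reason to replace the floatie, but it acts on that one event late.

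What is at stake is safety. The enrolled children are pre-locomotor, and the device is meant to carry them without being held. If support is lost in the water, the outcome to be feared is the one the plan itself names. The possible harm is grave even where the event is unlikely, and the preventive step is very cheap. The primary outcome, its comparison across the three four-week periods and the descriptive analysis are unaffected.

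**Working it through.** The plan gives no figure to reproduce: no deflation rate, no number or length of sessions, and no failure count. The check is therefore a reading of the rule, followed by limits on its scale.

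**Step 1: named cause against stated response (Potential risks).**

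| Situation | Stated response | Does it remove the cause? |
|---|---|---|
| First deflation, from a leak | Stop, re-inflate the same unit, resume | No |
| First deflation, from a breaking seam | Stop, re-inflate the same unit, resume | No |
| Second deflation of that unit | Replace | Yes, a new unit is supplied |

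That air does not mend a leak or a seam is an inference, but a safe one. No other section of the document changes the rule.

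**Step 2: what re-inflation can detect.** The replacement promise is not limited to deflation in the water. A fast leak that shows while the unit is being refilled therefore triggers replacement before the child returns. A slow leak, or a seam that opens only under load, may hold at refilling and fail later in use. This second path is the remaining gap.

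**Step 3: limits on scale.** Inputs: up to 4 children (Approach), use from week 4 to week 8 and one floatie per family (Procedures).

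- Planned exposure: 4 × (8 − 4) = 4 × 4 = 16 child-weeks at most.
- First units: 4 × 1 = 4 at most.
- Repeat deflations of the same unit allowed before replacement, in or out of the water: 2 − 1 = 1 per unit under the present rule, so at most 4 × 1 = 4. Under replacement at the first deflation: 1 − 1 = 0.

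These are ceilings, not expected counts. Few events, if any, are likely.

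**Step 4: extra floaties, first units only, in-use trigger.** Compare the two rules for a unit that deflates:

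- never: 0 − 0 = 0 extra;
- exactly once: 1 − 0 = 1 extra;
- twice: 1 − 1 = 0 extra, since the present rule also replaces it.

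The extra cost equals the number of first units that would deflate exactly once, so it lies between 0 and 4. Replacement for unexplained air loss outside use could add slightly to this.

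**The case against.** The strongest case against the point has five parts.

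- **The working instruction is in a document we do not have.** Potential risks reports what the consent form tells caregivers. A reader might infer that nothing beyond re-inflation stands between a first deflation and the child's return to the water. The documents do not support that: the consent form may contain a leak check or a waiting period. What stands is narrower. The plan's own text sets replacement at the second deflation.
- **Re-inflation is a partial test.** This is correct, as step 2 shows, and it narrows the gap to slow leaks and weakened seams. It does not close it.
- **Supervision covers the hazard.** A reader might infer that supervision comes into play only after air is lost. In fact it is required throughout use and is already in place when a deflation starts. It limits the harm from a deflation, but it does not take a suspect unit out of use.
- **A family could be left with a defective floatie.** This too might be inferred, since the family keeps the unit. However, a unit still in use at week 8 under the present rule has not qualified for replacement since its first deflation, so it either held air or was little used. That is weak evidence of a defect, and the point does not rely on it. Nor does the text say where the floatie sits on the body, so nothing is argued from its position relative to the child's head.
- **A poorly closed valve could be the cause, and refilling would cure it.** That is possible. The plan names only leaks and seams, and its text gives the caregiver no way to tell these apart from a valve left open. The proposed wording allows for an open valve when air is lost outside use.

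**Conclusion.** The point holds in this form: for the causes the plan itself names, the stated rule lets a unit that has deflated once go back into use unrepaired, and replacement at the first deflation would be safer. The residual risk is small and cannot be quantified from the documents. The only available limits are 16 planned child-weeks and one permitted repeat deflation per first unit, against none under the proposed rule.

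This is a change the sponsor should make, not a fatal flaw. The recommendation rests on the gravity of drowning and the low cost of prevention, not on evidence that deflations are frequent. It assumes that the paragraph in Potential risks fairly states the rule in force and that deflations arise from the causes named there. If the consent form already tells caregivers to withdraw the unit at the first deflation, only the protocol text needs to be brought into line.

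**What to change.** In Potential risks, keep the supervision sentence and the reference to the consent form. Replace the re-inflate and replace rule with wording such as:

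> If the floatie begins to lose air during use, or loses air at any other time without an evident cause (such as an open valve), the consent form instructs the caregiver to take the child out of the water, not to use that unit in water again, and to contact the study team, which will replace it.

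The second trigger is needed because the present promise of replacement is not confined to deflation during use. A rule limited to use would leave a unit that goes soft between sessions with no stated remedy. Align the consent form if it does not already say this.

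**Cost.** A short IRB amendment; 0 to 4 extra floaties for the first units from the in-use trigger, and slightly more if units lose air outside use; a call between visits; a few missed sessions while a replacement arrives; and the occasional replacement of a sound unit. With a risk the plan calls small, one spare is probably enough. Missed sessions would show in the activity log, which already records dates and durations of use. No visit, outcome or analysis changes.
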